Chief Investigator	[name] Metabolic Research Laboratories and MRC Metabolic Diseases Unit University of Cambridge WT-MRC Institute of Metabolic Science (Level 4) [name] [contact] [contact]; [name]
Study Co-ordinator	[name], details as above
Sponsor	Cambridge University Hospitals NHS Foundation Trust and University of Cambridge [name] R&D Manager Cambridge University Hospitals [name] [contact] [contact] Email: r&[contact]
Funder(s)	Wellcome Trust Cambridge Biomedical Research Centre Seed Fund
Key Protocol Contributors	[name] [name] [name] [name] [name] [name]

Gastrectomy, eating behaviour and GLP-1

STUDY SUMMARY

Study Title	The effect of glucagon like peptide-1 (GLP-1) on glycaemic profile and eating behaviour following gastrectomy
Internal ref. no. (or short title)	Gastrectomy, eating behaviour and GLP-1 (GaS)
Study Design	Double blind, randomised, crossover physiological study.
Study Participants	16 patients who have undergone total gastrectomy
Planned Size of Sample (if applicable)	16
Follow up duration (if applicable)	3 study visits (one screening, two intervention)
Planned Study Period	2 years
Research Question/Aim(s)	To investigate the role of GLP-1, an incretin gut hormone, on the altered eating behaviour and glucose homeostasis experience following gastrectomy.

Gastrectomy, eating behaviour and GLP-1

FUNDING AND SUPPORT IN KIND

FUNDER(S)	FINANCIAL AND NON FINANCIAL SUPPORT GIVEN
(Names and contact details of ALL organisations providing funding and/or support in kind for this study)	
Wellcome Trust	Part of the joint investigator award of [name] and [name]
Wellcome Trust / NIHR Addenbrooke's Clinical Research Centre	All participant facing work will be carried out in the core funded ACRC, and so benefit from the core grants awarded to this facility within Cambridge University Hospitals from the Wellcome Trust / NIHR

Gastrectomy, eating behaviour and GLP-1

ROLE OF STUDY SPONSOR AND FUNDER

The University of Cambridge and Cambridge University Hospitals NHS Foundation Trust are co-sponsors of this study. The sponsors provide oversight of study design and implementation, as well as providing the facilities required for the study and access to the necessary patient populations. The sponsors have no control over the final decisions regarding data analysis or interpretation, or publication of the research findings.

1 BACKGROUND

It is well established that surgery on the upper gastrointestinal tract profoundly alters appetite, weight and glucose homeostasis. This is harnessed in the treatment of obesity and type two diabetes¹ but can have significant deleterious effects in the lean population undergoing surgery for cancer². At present, there is no adequate understanding of the pathophysiological basis of these changes, although it is suspected that gut hormones, bile acids and neuro-cognitive factors may play a role^{3,4}.

Approximately 2500 gastric and oesophageal resections are carried out annually in the UK for cancer, with a 50% five year survival rate. Long-term quality of life after gastrectomy is known to be poor, with a high prevalence of “dumping syndrome”, a poorly understood constellation of symptoms². There is no effective treatment, or indeed understanding of the underlying cause, of these symptoms. This is a significant unmet need in the field of cancer survivorship.

The role of the (Glucagon-like-peptide-1) GLP-1 – insulin axis in the resolution of obesity and diabetes after bariatric surgery has been studied by several groups, and is suspected to play a role in the severe hypoglycaemias seen by some patients⁵. No one to date has assessed the role of GLP-1, a gut derived hormone responsible for potentiating the insulin response and suppressing appetite, in the symptoms seen after gastrectomy for cancer. A pilot study run by our group has demonstrated significantly elevated levels of GLP-1 and insulin, and altered appetite and satiety responses, in a cohort of five post-gastrectomy patients. The exact physiological effect of the GLP-1 elevation is however less clear, and temporary blockade of the GLP-1 axis will allow us to define the physiological changes resulting from GLP-1 secretion versus other altered physiological pathways in this group.

This study is a double-blind, crossover physiological study of the effects of excess GLP-1 secretion on glycaemic profile and cognitive eating behaviour factors in the post-gastrectomy population.

Participants will attend for two study visits, on one occasion receiving an infusion of Exendin 9-39, a peptide antagonist of GLP-1 action, and on the other a placebo infusion. They will undergo a glucose tolerance test including serial blood tests and measures of hunger and satiety, and then have an ad libitum meal, with measurement of amount and speed of eating, as well as simple cognitive tasks to assess food / reward behaviour. These tasks include food-related attentional bias using a dot-probe task⁶ and food-motivation behaviour using a validated grip-strength measurement task⁷.

Exendin 9-39 is a peptide that has been used by several groups in the USA and Europe to investigate the effects of GLP-1 on physiological and cognitive factors, with no published serious adverse events. It has not previously been used in the gastrectomy population, but has been used in healthy volunteers and patients who have undergone bariatric surgery. It has an extremely short half-life and the effects cease within several minutes of cessation of the infusion. It is not at present a licensed medication, and is available for use as an investigative compound, manufactured to GMP standard by Bachem AG. Based on a review of the literature, and advice from a group at Stanford University who have used Exendin 9-39 infusions in the post-bariatric surgery population, the infusion will be commenced with a bolus of 7500pmol/kg and run at a rate of 500pmol/kg/minute.

The assessment of food and reward behaviour, and glucose homeostasis, requires controlling for confounding factors. These include diabetes and depression and will be assessed prior to study participation.

2 RATIONALE

At present, there is no physiological understanding of the altered glucose homeostasis and eating behaviour seen in patients after gastrectomy. There is a growing population of patients surviving long-term after surgery for gastric cancer, including some in their teens and twenties who have undergone prophylactic surgery for high risk genetic mutations. Our group works with the researchers leading the Familial Gastric Cancer Study, who provide clinical care, and research, for the familial gastric cancer population in the UK. This group has identified, through patient seminars, the need for further research into the long-term consequences of gastrectomy as a key priority.

This study aims to assess the role of one specific hormone, GLP-1, which is known from our pilot data to be excessively secreted in response to food in this population. Ultimately, a better understanding of this pathway may lead to novel investigative and treatment paradigms, for a condition presently lacking either.

3 THEORETICAL FRAMEWORK

We hypothesize that blockade of the GLP-1 axis using Exendin 9-39 in the post-gastrectomy population will:

1. Ameliorate the excessive post-prandial insulin response seen in this patient group, as evidenced during a 50g oral glucose tolerance test by:
 - a. Increased nadir blood glucose
 - b. Reduced total insulin secretion
2. Ameliorate the increased satiety signalling and consequent effects on food intake, hunger and satiety, and food motivation during and after an ad libitum meal, as evidenced by:
 - a. Increased eating rate and food intake during ad libitum meal
 - b. Increased hunger and decreased satiety ratings during and immediately after the ad libitum meal
 - c. Increased attention to and motivation for food both prior to and after the ad libitum meal

4 RESEARCH QUESTION/AIM(S)

4.1 Objectives

1. To identify the role of the excessive GLP-1 secretion experienced by post-gastrectomy patients in the physiological and behavioural symptoms seen after gastrectomy:
 - a. Post-prandial hypoglycaemia
 - b. Altered hunger / satiety scores
 - c. Altered food attention bias and reward behaviour
 - d. Altered food motivation and intake at ad libitum meal

4.2 Outcome

The key outcome of this study is the understanding of the physiological effects of excessive GLP-1 secretion seen in the gastrectomy population. To this end, Exendin 9-39, which is an antagonist of GLP-1 activity, will be used to block GLP-1 activity. This is a physiological study of the actions of GLP-1, not an investigation of the effects of Exendin 9-39.

5 STUDY DESIGN and METHODS of DATA COLLECTION AND DATA ANALYSIS

Each participant will attend for three visits – a screening visit and two study visits (matched visits, one with placebo infusion and one with Exendin 9-39 infusion).

Screening visit

The purpose of this visit is to ensure there are no comorbidities which may be exacerbated by, or confound, the study protocol. The participant will have the study explained to them, be asked to consent to participation and then be asked a full medical and surgical history, and receive blood and cognitive screening tests as detailed:

Blood tests – Full blood count, thyroid function, renal function, HbA1c (diabetes screen).

Validated questionnaire tools – Three factor eating questionnaire, Barratt's impulsivity scale, PHQ9 and GAD7 for anxiety and depression, Dumping severity score

Demographic measures – Age, past medical history, details of gastrectomy and other associated treatments (chemotherapy or radiotherapy), current medications, family history, height, weight, waist / hip circumference.

Symptomatic measures – free discussion of participant reported post-gastrectomy consequences, changes in eating behaviour and food preference and behavioural adaptations.

Study visit

Participants will be admitted to the Clinical Research Facility at Addenbrooke's Hospital the night prior to each study visit, to allow for provision of a standard meal and commencement of the study soon after waking the following morning. Participants will receive an infusion of either placebo (1% human albumin in sterile water) or Exendin 9-39 (dissolved in 1% human albumin in sterile water), with an initial bolus of 7500pmol/kg and at a rate of 500pmol/kg/minute. Participants and investigators will be blinded to the infusion contents, with the infusion schedule randomised by sealed envelopes prepared in advance. We will use a balanced randomisation protocol, with half of participants undergoing placebo at their first visit. Visit schedule and interventions are as the table below, with discharge at approximately 1700, after the post-infusion meal. Participants will be provided with a symptom diary during and for twenty four hours after the visit to monitor for any adverse events.

All female participants of child-bearing age are to receive a urinary pregnancy test on each infusion visit.

Key study measures are:

1. Continuous glucose monitor – a Dexcom G4 continuous subcutaneous glucose monitor will be used to measure interstitial glucose levels at 5 minute intervals. This is a key outcome measure, as well as a safety measure to monitor for hypoglycaemia during the OGTT. The device is CE marked for the monitoring of glucose profile and in widespread use.
2. Blood tests – blood will be collected and centrifuged, and plasma assayed for hormonal mediators of glucose homeostasis (including insulin, glucagon and GLP-1). Maximum volume of blood collected across 3 visits will be 250ml.
3. Simple reaction time task – a straightforward measure of reaction time wherein a participant clicks a key in response to a stimulus on a computer screen, will act as a control / baseline measure to identify between and intra-participant variability in response times that may influence other cognitive tasks.

Gastrectomy, eating behaviour and GLP-1

4. Visual analogue scales – participants will be asked to mark how hungry, sated or nauseous they feel on a 10cm visual analogue scale.
5. Sigstad score – a validated measure of post-gastrectomy symptoms, to be completed on a tick box sheet during the OGTT.
6. Attention bias task – participants will be asked to fixate on a central mark on a computer screen, and will then be shown two images conflicting as to their depiction of food (i.e. food vs not food, or high energy vs low energy food), under one of which appears a dot. The speed with which they indicate the side of the dot, with regard for the associated image, identifies their degree of food attention bias.
7. Food motivation task – a validated measure of food motivation, using grip strength as a measure of degree of work the participant will undertake to receive particular food related rewards and stimuli.
8. Eating rate / food intake – a universal eating monitor (a set of hidden scales placed beneath a meal) will examine rate and amount of consumption of a standard ad libitum meal.
9. Liking ratings – visual analogue scales of how much the participant likes the meal.

All questionnaires and tasks are validated.

Data will be collected in paper format, stored in a locked cabinet in a secure area of Addenbrooke's Hospital, and transcribed in anonymous fashion to a database on a secure University of Cambridge server. Data storage and analysis will be carried out using Microsoft Excel and R.

Exendin 9-39 will be sourced from Bachem AG, who produce GMP grade Exendin 9-39 with appropriate supporting documentation and guarantees. It will be stored as per supplier guidance in the Addenbrooke's pharmacy, or another appropriate secure storage area, and made up to a standard dilution in 1% human albumin in 0.9% sterile saline. Randomisation will be administered by means of sealed envelopes, with each visit provided with either an infusion of Exendin 9-39, or placebo (1% human albumin in 0.9% sterile saline). Both infusions will be at a rate determined by the weight of the participant and stock concentration of Exendin 9-39, and provide a 7500pmol/kg (25.27 μ g/kg) bolus of Exendin 9-39 followed by a 500pmol/kg/minute (1.685 μ g/kg/minute) infusion. Infusions will be administered through an appropriately maintained clinical infusion pump on the CRF.

Gastrectomy, eating behaviour and GLP-1

Approximate time	Task	Test	Infusion
0800	Insert continuous glucose monitor and venous cannula		
0820	Fasting bloods and cognitive measures	Blood sample, simple reaction time task, visual analogue scales (VAS) for hunger, satiety, nausea, Sigstad	
0840	Start infusion		
0900	Fasting / blockaded measures	Blood sample, simple reaction time task, attention bias, food motivation, VAS, Sigstad	
0910	50g oral glucose drink (OGTT)		
0925	OGTT measures	Blood sample, VAS, Sigstad, attention bias	
0940	OGTT measures	Blood sample, VAS, Sigstad, food motivation	
0955	OGTT measures	Blood sample, VAS, Sigstad, simple reaction time task	
1010	OGTT measures	Blood sample, VAS, Sigstad	
1025	OGTT measures	Blood sample, VAS, Sigstad, (SRTT if hypoglycaemic)	
1040	OGTT measures	Blood sample, VAS, Sigstad	
1045	Post-OGTT cognitive tasks	Attention bias, food motivation, simple reaction time task	
1115	Bloods then ad libitum meal, VAS at 5 minute intervals, liking ratings twice (5 minutes into meal, and at completion of meal)	Blood sample, universal eating monitor, VAS, liking ratings	
1200 OR 10 minutes after completion of meal	Post meal bloods and cognitive tasks, then stop infusion (approx. 1230)	Attention bias, food motivation, bloods	
1230 until next meal (appr 1700)	Hunger / satiety scores every 30 minutes, meal then discharge	VAS	

Study visit timeline

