7 SAMPLE AND RECRUITMENT

7.1 Eligibility Criteria

7.1.1 Inclusion criteria

Participants must be:

- At least 3 months post completion of treatment for gastric cancer, or prophylactic gastrectomy
- Aged at least 18 years
- Able to tolerate an oral glucose tolerance test
- Able to understand and retain all information regarding the study and give informed consent.
- Willing to receive an infusion of human albumin solution

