7.2 Sampling

7.2.1 Size of sample

Up to sixteen participants will be recruited for this study, each to complete one screening and two randomised study visits (placebo and Exendin 9-39). Previous data shows a between visit correlation of glucose measurement of 0.52, with standard deviation of 0.5. Salehi et al demonstrated mean nadir blood glucose of 3.9mmol/L (standard deviation 0.6) with GLP-1 blockade and 2.6mmol/L (0.6) with placebo in post-bariatric surgery patients⁵. Based on this data, we have conservatively estimated an effect size of 0.5 (based on mean change in nadir glucose of 0.5mmol/L. To detect this change with 90% power at a 5% significance level requires a sample size of 13. The recruitment of sixteen participants will allow for drop outs, and for the possibility that more data will be required to reach significance in the previously unstudied (in this group) outcomes of food motivation and reward behaviour.

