8 ETHICAL AND REGULATORY CONSIDERATIONS

8.1 Assessment and management of risk

This is a physiological study, using a well described test (oral glucose tolerance test) with a blinded infusion of a peptide or placebo.

Oral glucose tolerance testing (OGTT) in this group has been carried out by our and several other groups. There is a risk of hypoglycaemia developing during the test period, for which the participant will be closely monitored using a continuous subcutaneous glucose monitor. A robust protocol is in place for the management of hypoglycaemia during an OGTT in this population, including the administration of intravenous glucose, or glucagon, should this be necessary (in our experience, this has never occurred). Other risks of the study visit and OGTT include pain and bruising at the cannulation site.

[figure not shown]
Exendin 9-39 has been used by multiple groups in Europe and the USA, with published results from 259 infusions in 240 participants^{4,8-22}. No serious adverse events have been ascribed to the use of Exendin 9-39, which is unsurprising given it is a highly selective blocker of the GLP-1 receptor with a very short half-life. It is however possible that the participant may manifest an allergic reaction to the peptide, or to the human albumin in which it is dissolved. To facilitate early diagnosis and appropriate treatment should this occur, all participants will be closely monitored by dedicated nurse and doctor during the infusion. The study will take place on a clinical research ward within Addenbrooke's Hospital, with full resuscitation equipment and access to the hospital's emergency medical team should it be necessary. The CRF has experience in running phase 1 clinical trials, including first in human studies, which carry a greater burden of risk than this proposed study.

Gastrectomy, eating behaviour and GLP-1

All adverse events (AEs) will be recorded as per the table and figure below. During study visits, participants will be questioned regarding adverse symptoms, and asked to keep a symptom diary for 24 hours post visit to ensure all AEs are recognised. All non-serious AEs will be documented and submitted in the annual safety report.

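### The protocol names two different diluents for the same intravenous infusions: sterile water in one paragraph of Section 5, 0.9% saline in another

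*Combined protocol and SAP*

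**What the plan says.** Section 5 describes the vehicle twice.

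- The opening paragraph under Study visit says participants receive "placebo (1% human albumin in sterile water) or Exendin 9-39 (dissolved in 1% human albumin in sterile water"). The dose given there is a 7500 pmol/kg bolus, then 500 pmol/kg/min.
- The preparation paragraph, after the numbered list of key study measures, covers sourcing, storage and making up. It has Exendin 9-39 "made up to a standard dilution in 1% human albumin in 0.9% sterile saline" and defines the comparator as "placebo (1% human albumin in 0.9% sterile saline"). On the pump setting, it adds that "Both infusions will be at a rate determined by the weight of the participant and stock concentration of Exendin 9-39".

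Two other places mention the vehicle without naming the diluent. The inclusion criteria (7.1.1) ask only that participants be "Willing to receive an infusion of human albumin solution". The risk section (8.1) refers to possible allergy to the peptide "or to the human albumin in which it is dissolved".

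The amendment history (Appendix 2) has no entries, so neither description is marked as superseded.

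**The concern.** Sterile water and 0.9% saline cannot both be the diluent of one preparation. Each paragraph names its diluent twice, once for each infusion, so a single misplaced word does not explain the difference.

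The stake is correct preparation and participant safety. The two fluids differ by their whole salt content. Someone who prepares the infusion from the visit paragraph as written would make a hypotonic intravenous fluid. The risk section considers allergy to the peptide or the albumin but does not consider tonicity.

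The point does not concern bias. Within each paragraph the placebo and active vehicles match.

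**Working it through.** **1. The two paragraphs side by side**

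| Element | Visit paragraph | Preparation paragraph |
|---|---|---|
| Exendin 9-39 vehicle | 1% albumin in sterile water | 1% albumin in 0.9% saline |
| Placebo vehicle | 1% albumin in sterile water | 1% albumin in 0.9% saline |
| Bolus | 7500 pmol/kg | 7500 pmol/kg (25.27 µg/kg) |
| Rate | 500 pmol/kg/min | 500 pmol/kg/min (1.685 µg/kg/min) |

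**2. Do the plan's own dose figures agree?** Molar mass = mass / amount.

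- Bolus: 25.27 µg / 7500 pmol = 3369 g/mol.
- Infusion: 1.685 µg / 500 pmol = 3370 g/mol.

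They agree with each other, and the dose is the same in both paragraphs. Of the elements compared, only the diluent conflicts.

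**3. How different are the fluids?** These are ideal values.

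- 0.9% saline: 9 g/L / 58.44 g/mol = 154 mmol/L sodium chloride; × 2 ions = about 308 mOsm/L.
- 1% albumin: 10 g/L / 66,500 g/mol (assumed molar mass) = 0.15 mmol/L.
- Sterile water: 0.

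The albumin stock may carry some salt, but it is not described. If the stock were isotonic (assumed), dilution to 1% would leave:

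- from a 20% stock (assumed): 308 × 1/20 = about 15 mOsm/L;
- from a 5% stock (assumed): 308 × 1/5 = about 62 mOsm/L.

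Under each of these assumptions the sterile-water version stays far below 308 mOsm/L.

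**4. How long, and how much drug?** In the visit timetable the infusion starts at 0840 and stops at about 1230, which is 230 minutes.

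- Dose per infusion visit: 25.27 + 1.685 × 230 = 412.8 µg/kg.
- At an assumed 70 kg: 412.8 × 70 = 28.9 mg.

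**5. How much fluid?** Volume = dose / concentration. The documents give no concentration, so the values below are assumptions chosen to show the range. They are not estimates for this trial.

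| Assumed weight | At 1 mg/mL | At 0.1 mg/mL |
|---|---|---|
| 50 kg | 21 mL | 206 mL |
| 70 kg | 29 mL | 289 mL |
| 90 kg | 37 mL | 372 mL |

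At 70 kg, averaged over the 230 minutes, that is 28.9 / 230 = about 0.13 mL/min at 1 mg/mL, or 289 / 230 = about 1.3 mL/min at 0.1 mg/mL. Placebo runs at a rate set the same way, so its volume matches.

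**6. How many infusions?** Section 7.2.1 states that "Up to sixteen participants will be recruited for this study", each with two infusion visits: 16 × 2 = 32 at most.

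**The case against.** The strongest reply is that the intended vehicle is not really in doubt. The preparation paragraph is the only text on making up the product. It names saline for both infusions, gives the doses by mass and explains how the pump rate is set. The visit paragraph mentions the vehicle only in parentheses. A pharmacist would probably work from the former, and pharmacy procedures might catch the discrepancy.

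That is a fair reading, and it is why saline is the proposed correction. It does not remove the conflict, because the protocol does not say which paragraph governs. Nor does it say who prepares the infusions, and it allows the product to be stored outside the hospital pharmacy.

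A second reply is that the safety case is not quantified. Clinical effect depends on volume, and the volumes above rest on assumed concentrations and span about 18-fold (21 to 372 mL). This stands: at the low end the fluid load is small. The near-zero osmolality is also a lower limit that ignores salt carried over from the albumin stock, as step 3 shows. What survives is that the sterile-water version is markedly hypotonic, and that the documents give no volume from which to call this trivial.

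Third, nothing changes for inference. That is accepted in full: sample size, power, significance level and blinding are untouched, provided one vehicle is used at every visit.

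**Conclusion.** The concern holds. The protocol gives two incompatible vehicles for both infusions, and nothing in it settles which applies. The difference is about 308 mOsm/L from the diluent against none, or roughly 15 to 62 mOsm/L overall if an isotonic albumin stock of 20% or 5% is assumed. It bears on infusions of about 230 minutes, at most 32 of them.

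The textual conflict rests on no assumption. The tonicity figures assume ideal solutions and an albumin molar mass of about 66.5 kg/mol. The clinical consequence cannot be sized without the infused volume, and no particular harm is asserted. That saline was intended is an inference from the more detailed paragraph, which the sponsor must confirm.

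This should be corrected before first dosing. It is an error in the specification of an intravenous product, not a threat to the trial's conclusions.

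**What to change.** Have pharmacy confirm the vehicle against the supplier's documentation for Exendin 9-39. Then, in the opening paragraph under Study visit in Section 5, replace sterile water with 0.9% sterile saline in both places, so that it agrees with the preparation paragraph. If pharmacy finds that another vehicle is required, state that one in both paragraphs.

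The cost is a correction to one sentence and one pharmacy check. The design, sample size and analysis do not change.

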6 STUDY SETTING

The study will be performed in the Wellcome Trust-NIHR Clinical Research Facility at Addenbrooke's Hospital. The staff and infrastructure of the CRF bring considerable expertise and experience in research involving metabolic factors and infusion of blinded agents. Each study visit will be supported by at least a dedicated nurse and doctor for the duration of the visit.

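### The live glucose trace may partly reveal allocation before the later self-rated and effort-based measures, and nothing in the plan keeps it from the participant or the staff running them

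*Combined protocol and SAP*

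**What the plan says.** The study is described as double blind. Section 5 (Study visit) states: "Participants and investigators will be blinded to the infusion contents".

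Item 1 of the key study measures in section 5 introduces a continuous glucose monitor that "will be used to measure interstitial glucose levels at 5 minute intervals" and names it as one of the key outcomes, "as well as a safety measure to monitor for hypoglycaemia during the OGTT". Section 8.1 names hypoglycaemia as a risk of the glucose test, "for which the participant will be closely monitored using a continuous subcutaneous glucose monitor", and refers to a separate hypoglycaemia protocol.

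The study visit timeline in section 5 makes one scheduled step conditional on glucose status: the 1025 row lists, in brackets, "SRTT if hypoglycaemic", meaning an extra simple reaction time task.

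On staffing, section 6 says: "Each study visit will be supported by at least a dedicated nurse and doctor for the duration of the visit". The protocol does not say which of these people watches the monitor, whether the participant can see it, who runs the ratings, grip task and meal, or whether blinding will be checked.

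**The concern.** Hypothesis 1a in section 3 predicts a higher nadir glucose under Exendin 9-39. The live safety signal is therefore expected to differ between the two visits, and anyone who sees it has a clue to the infusion. The extra task at 1025 can pass the same clue to the participant, because its presence signals a low reading.

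Hypothesis 2 is tested later in the same visit through hunger and satiety ratings, food attention, grip effort and meal intake, with liking ratings also taken at the meal. Ratings and voluntary effort can shift with what the participant expects and with how staff behave. If a participant or a member of staff suspects the allocation by then, a difference between visits could partly reflect expectation rather than GLP-1 blockade.

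**Working it through.** **Inputs.** All from section 7.2.1 of the protocol: between-visit correlation r = 0.52; SD 0.5; planned difference in nadir 0.5 mmol/L; cited post-bariatric nadirs 3.9 (SD 0.6) with blockade and 2.6 (SD 0.6) with placebo, a difference of 1.3; 90% power, 5% significance, n = 13; up to 16 recruited. Clock times are from the study visit timeline in section 5.

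**Step 1: the plan's own figure.** SD of the within-person difference = 0.5 × √(2 × (1 − 0.52)) = 0.490. Standardised difference = 0.5 / 0.490 = 1.02. A two-sided paired t-test at 5% first exceeds 90% power at n = 13 (92.1%; 91.7% with a period term). The stated 13 is reproduced, so these inputs are used as the plan uses them.

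**Step 2: which measures come after the clue.** The glucose drink is at 0910. The documents give no time for the nadir.

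| Time | Minutes after drink | Self-rated, effort and task measures | Exposed? |
|---|---|---|---|
| 0820, 0900 | before | VAS, Sigstad; at 0900 also attention and grip | No |
| 0925, 0940 | 15, 30 | VAS, Sigstad, attention (0925), grip (0940) | Probably not |
| 0955–1040 | 45–90 | VAS, Sigstad | Possibly, later in the window |
| 1045 | 95 | Attention, grip, reaction time | Yes |
| 1115 | 125 | Meal intake, VAS, liking | Yes |
| about 1200 | about 170 | Attention, grip | Yes |
| 1230 to about 1700 | 200 or more | VAS | Yes |

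**Step 3: how informative the nadir is.** Assume normal nadirs, equal SDs, a reader who knows the two condition means, and no sensor error. Half the participants receive placebo first, so chance is 50%.

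- One visit, cutting at the midpoint of the means: P(correct) = Φ(difference / (2 × SD)).
  - Planned values: Φ(0.5 / 1.0) = Φ(0.50) = 69%.
  - Cited values: Φ(1.3 / 1.2) = Φ(1.08) = 86%.
- Both visits, calling the higher nadir Exendin 9-39: P(correct) = Φ(difference / (SD × √(2(1 − r)))).
  - Planned values, r = 0.52: Φ(0.5 / 0.490) = Φ(1.02) = 85%.
  - Cited values, r = 0.52 (assumed to carry over): Φ(1.3 / 0.588) = Φ(2.21) = 98.6%.
  - Cited values, r = 0: Φ(1.3 / 0.849) = Φ(1.53) = 93.7%.

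In 16 participants the planned values give 16 × 0.691 = 11.1 expected correct guesses from one visit and 16 × 0.846 = 13.5 from both, against 8 by chance.

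**Step 4: a reader who does not know the means.** If the one-visit cut is misplaced by 0.5 mmol/L on the planned values, accuracy is (Φ(1.5) + Φ(−0.5)) / 2 = (0.933 + 0.309) / 2 = 62%.

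**The case against.** Three stronger readings are tempting, and the documents do not support them.

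- *Blinded staff themselves act on the trace.* A reader might infer this, but no section says who watches the monitor. The 1025 row does not name the monitor either. Live viewing by someone follows from item 1 of the key study measures and section 8.1; that it is the person running the tasks does not.
- *The trace discloses allocation.* The clue is probabilistic. The two-visit figures can apply only late in visit 2, and the one-visit figure falls when the means are unknown. Section 1 says Exendin 9-39 has not been used after gastrectomy, so they are not well known. Against that, sections 7.2.2 and 7.3 select people with suspected or proven post-prandial hypoglycaemia, some from glucose tests run by the study team, so some untreated results may be known beforehand.
- *Every hypothesis 2 outcome is biased.* The 0820 and 0900 measures precede the drink, and those at 0925 and 0940 probably precede the nadir. Hypothesis 2c covers attention and motivation before as well as after the meal, so part of its data is unaffected. Meal intake is recorded on hidden scales and attention bias by computer reaction time, which makes both less open to influence than ratings or grip effort. Nadir glucose itself is instrument-measured.

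It is also fair to say that safety viewing is necessary, that the SD of 0.5 is given for glucose measurement in general and not for a monitor nadir, and that symptoms may unblind some participants whatever is done with the display. All of this stands. It narrows the point without removing it: an arm-dependent signal is read live, and the plan does not stop it reaching people whose ratings, effort or conduct could respond to it.

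**Conclusion.** The concern holds in limited form. Following the plan as written, the glucose trace may partly unblind the participant or task staff before the hypothesis 2 measures from 1045 onward, and possibly before the late glucose-test VAS and Sigstad scores. VAS, liking ratings and grip effort are the most exposed.

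The trace is clearly informative at the planned effect (69% from one visit, 85% once both can be compared). It comes close to decisive only if the effect is as large as in the cited post-bariatric study (86%, then 94–99% for r from 0 to 0.52). These figures rest on the assumptions in Step 3 of the working. They describe how well allocation could be guessed; they do not estimate a shift in any outcome, and the documents give no basis for one. Whether the clue actually reaches the people concerned depends on staff roles that the protocol leaves open.

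**What to change.** Add to section 5 of the protocol:

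> The glucose monitor display and alarms are watched by the staff member responsible for safety. They are not visible to the participant or to whoever runs the VAS, attention, motivation and meal tasks, and readings are not disclosed to either unless safety requires it.

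In the timeline, run the 1025 reaction time task in every participant at both visits, so that its presence no longer signals glucose status. Without this change the masking rule would conflict with the schedule, because whoever runs a conditional task must learn why it is being run.

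At the end of each visit, record the participant's and the task investigator's guess of allocation, and report these with the results.

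The response to hypoglycaemia is left as it is.

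Cost: protocol wording, one short computer task per visit, two recorded guesses, and a division of roles between the nurse and doctor already assigned, with a third person if both are needed for safety. The person watching glucose may be partly unblinded and should not run the tasks. Symptoms may still give some clue; the recorded guesses would help show how far blinding held.
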